**Study protocol: Treatment Outcomes of DOACs in CVT: A Prospective Study in Vietnam**

- Patients already receiving anticoagulation therapy for another underlying condition at the time of CVT diagnosis

## 5. METHODS

### 5.1. Study endpoint

#### 5.1.1. Primary study endpoint

The primary endpoint of the study is a composite outcome assessed over a 6-month follow-up period, comprising: (1) the occurrence of VTE, including recurrent CVT, deep vein thrombosis of any limb, pulmonary embolism, or thrombosis involving the splanchnic, jugular, caval, renal, or catheter-related veins; and (2) major bleeding events, defined according to the criteria established by the International Society on Thrombosis and Haemostasis (ISTH) (see Appendix B).

#### 5.1.2. Secondary study endpoint

##### **Assessed at 3 and 6 months ( $\pm$ 1 month):**

- Functional outcome: defined as a score of 0–1 on the Modified Rankin Scale (mRS). The mRS ranges from 0 (no symptoms) to 6 (death). Lower scores reflect better functional recovery.
- Number of participants with major bleeding events: defined according to the criteria established by the International Society on Thrombosis and Haemostasis (ISTH) (see Appendix B)
- Number of participants with clinically relevant non-major bleeding (CRNMB) events: defined according to the criteria established by the International Society on Thrombosis and Haemostasis (ISTH) (see Appendix B)
- Number of participants with symptomatic recurrent VTE
- Health-related quality of life, measured by the EQ-5D-5L instrument and the Vietnamese population value set validated by Mai et al.
- Serial D-dimer measurements after CVT: plasma D-dimer levels will be measured at 3 and 6 months using a standardized quantitative assay. Values will be reported in ng/mL and interpreted in the context of post-CVT coagulation activity

##### **Assessed at 6 months ( $\pm$ 1 month):**

- Mortality Rate
- Number of participants who discontinued anticoagulant therapy early
- Number of participants with arterial thrombotic events
- Venous recanalization
- Frequency of chronic headache following CVT

## **5.2. Study procedures**

Baseline clinical and radiological data, including patient demographics, risk factors, imaging findings, anticoagulant treatment details, and in-hospital events during the acute phase of CVT, will be collected for all enrolled patients.

Participants will be followed up at 3 and 6 months after diagnosis. Data collected at these time points will include:

- Type and duration of oral anticoagulant therapy
- Clinical events, including recurrent thrombotic or bleeding events
- Degree of disability will be assessed using mRS
- Venous recanalization will be assessed at 6 months using brain MRI with venography or CT venography. Recanalization will be categorized as complete, partial, or none, based on the classification proposed by Aguiar de Sousa et al
- Health-related quality of life, evaluated using the EQ-5D-5L instrument. This tool evaluates five domains (mobility, self-care, usual activities, pain/discomfort, and anxiety/depression), each with five levels of severity. A utility index score will be calculated using the Vietnamese EQ-5D-5L value set, ranging from -0.511 to 1.000, where 1.000 indicates perfect health, 0.000 corresponds to death, scores below 0 indicate health states considered worse than death by the general Vietnamese population.
- Presence of chronic headache, defined as a headache occurring on  $\geq 15$  days per month and persisting for more than 3 months following the acute CVT event, consistent with the International Classification of Headache Disorders, 3rd edition

(ICHD-3). Headache-related disability, assessed using the Headache Impact Test (HIT-6)

All data will be collected as part of routine clinical care during outpatient visits or structured telephone interviews and recorded using standardized case report forms.

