## **2. OBJECTIVE**

### **Primary Objective**

To evaluate the effectiveness and safety of DOACs in patients with CVT over a 6-month follow-up period, using the composite outcome of major bleeding events or recurrent venous thromboembolism.

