## 4. ELIGIBILITY CRITERIA

### 4.1. Population

All consecutive adult patients diagnosed with CVT at Bach Mai Hospital were considered eligible for inclusion. Patients could be enrolled during initial hospitalization or through the outpatient stroke clinic. Both newly diagnosed cases and those referred from other facilities for further management were included.

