### 4.2. Inclusion criteria

- Signed informed consent (ICF) to participate in the study
- Age  $\geq$  18 years
- Confirmed diagnosis of cerebral venous thrombosis (CVT) based on clinical presentation and neuroimaging, including one or more of the following:

MRI and MRV, AND/OR

CT and CTV, AND/OR

MRI or CT combined with DSA

- Initiation of DOACs within 5 to 15 days after starting treatment with heparin

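### The only stated follow-up clock starts at diagnosis, but the cohort and the question start at the first DOAC dose 5 to 15 days after heparin; the primary endpoint has no rule for events before that dose

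*Protocol*

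**What the plan says.** - **Visits.** Protocol section 5.2: "Participants will be followed up at 3 and 6 months after diagnosis". Section 5.1.2 allows 1 month either side for the secondary endpoints, which include major bleeding and recurrent VTE. Section 5.1.1 states no window for the primary endpoint.
- **Entry.** Section 4.2 requires "Initiation of DOACs within 5 to 15 days after starting treatment with heparin". Section 4.1 adds "Patients could be enrolled during initial hospitalization or through the outpatient stroke clinic" and "Both newly diagnosed cases and those referred from other facilities for further management were included", so consent can come well after diagnosis.
- **Question.** Primary Objective: "To evaluate the effectiveness and safety of DOACs in patients with CVT over a 6-month follow-up period".
- **Analysis.** Section 6 treats the primary composite as time-to-event, with Kaplan-Meier curves and a cumulative rate at 6 months. It names no time zero. The Summary and section 5.1.1 also give a 6-month period without a start.
- **Events.** Section 5.1.1 counts "the occurrence of VTE, including recurrent CVT" together with ISTH major bleeding. Section 5.1.2 has the narrower "Number of participants with symptomatic recurrent VTE". Section 5.2 lists, with the baseline data, "in-hospital events during the acute phase of CVT, will be collected for all enrolled patients". It does not say whether these events enter the primary endpoint.
- **Bleeding definition.** Appendix B includes symptomatic intracranial bleeding, with no requirement that it be new or expanding. Section 4.3 does not exclude hemorrhage at presentation.

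**The concern.** The estimate is meant to describe DOAC treatment, yet the only clock in the protocol starts before any patient has taken a DOAC. Three things follow.

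1. A patient who dies, or becomes unsuitable for a DOAC, in the heparin phase never joins the cohort. Time from diagnosis to first dose is therefore partly guaranteed free of the worst events, which pulls the rate down. Entry through the outpatient clinic or by referral lengthens that guaranteed stretch for some patients.
2. A contact 6 months after diagnosis falls short of 6 months on the DOAC. An analysis plan can move the time origin, but it cannot recover follow-up that was never scheduled.
3. Non-fatal bleeding or VTE in the heparin phase, or symptomatic intracranial hemorrhage present at diagnosis, could be counted or left out by different adjudicators who both follow the text. Counting it charges the DOAC with events that preceded it.

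With a minimum of 69 patients and few expected events, one such decision is visible in the headline rate. The confidence interval does not reflect it, and a reader could not correct for it.

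**Working it through.** The protocol states no DOAC-exposed time and no expected event rate, and it justifies 69 patients by rarity and the single center. There is no figure of its own to reproduce on this point.

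**Inputs from the protocol:** 6 months (taken as 180 days); DOAC start 5 to 15 days after heparin (section 4.2); 1-month window (section 5.1.2, secondary endpoints only); 69 patients (section 5.3).

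**Assumptions, not in the protocol:** heparin starts on the day of diagnosis; risk of the composite is 6% per 180 DOAC days at constant hazard, with half and double shown; heparin-phase risk h is 1% to 3%.

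**1. Pre-DOAC share of the window.** 5/180 = 2.8%; 15/180 = 8.3%.

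**2. DOAC days D at the last contact.**

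| Contact | 15 heparin days | 5 heparin days |
|---|---|---|
| 5 months (day 150) | 135 | 145 |
| 6 months (day 180) | 165 | 175 |
| 7 months (day 210) | 195 | 205 |

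If heparin starts 3 days after diagnosis, the 6-month row becomes 162 and 172.

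**3. Effect of the shortfall.** Rate observed by day D = 1 - (1 - p)^(D/180).

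| p per 180 days | D = 165 | D = 175 | Loss in points |
|---|---|---|---|
| 3% | 2.75% | 2.92% | 0.25 and 0.08 |
| 6% | 5.51% | 5.84% | 0.49 and 0.16 |
| 12% | 11.06% | 11.69% | 0.94 and 0.31 |

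**4. Effect of counting heparin-phase events, same patients.** Rate = 1 - (1 - h) x 0.94^(D/180).

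| Heparin phase | Not counted | h = 1% | h = 2% | h = 3% |
|---|---|---|---|---|
| 15 days (D = 165) | 5.51% | 6.46% | 7.40% | 8.35% |
| 5 days (D = 175) | 5.84% | 6.78% | 7.72% | 8.66% |

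The comparison runs along a row. Counting adds 0.95 or 0.94 points at h = 1%, and 2.84 or 2.82 points at h = 3%. The 3% case is extreme. Over 5 days it implies a daily hazard of -ln(0.97)/5 = 0.0061, against -ln(0.94)/180 = 0.00034 on the DOAC, about 18 times as high. Over 15 days the ratio is about 6.

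**5. One misassigned event.** 1/69 = 1.4 points. For example, 4/69 = 5.8% (exact 95% CI 1.6-14.2%) against 5/69 = 7.2% (2.4-16.1%). At 6%, about 69 x 0.06 = 4 events are expected.

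**The case against.** **The effect is small.** The shortfall costs half a point or less at the assumed 6%, against an interval of 1.6-14.2% for 4/69. The 1-month window moves coverage by up to 30 days either way, more than the 5 to 15 days at issue, and a late visit already exceeds 180 DOAC days. This stands and limits the weight of the point. It does not remove it, because the schedule still lets an on-time or early contact fall short.

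**Time zero belongs in an analysis plan, and diagnosis is a legitimate clock.** In part this is right. A reader might infer that the protocol declares diagnosis as the Kaplan-Meier origin. It does not: section 5.2 times visits, and section 6 is silent. What holds is that diagnosis is the only origin stated anywhere. The visit schedule and the event definitions are protocol content.

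**Baseline events are already kept apart.** Section 5.2 files acute in-hospital events with baseline data, and Appendix B requires bleeding to be symptomatic. This protects in part. However, no text says that those events do not count, and hemorrhage present at diagnosis can be symptomatic. A reader might also infer that the Summary predicts such hemorrhage in this cohort. It only reports guideline advice on heparin; what can be said is that section 4.3 does not exclude these patients.

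**Pre-existing thrombosis is covered by the word *recurrent*.** Only in part. Section 5.1.1 attaches that word to CVT alone, not to deep vein thrombosis or pulmonary embolism. Sections 5.1.2 and 6 use it for VTE as a whole.

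**Conclusion.** The point holds as a modest but avoidable flaw. The protocol times follow-up from diagnosis, defines the cohort by a later event, asks about treatment that starts at that later event, and leaves open whether events in between count.

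At an assumed 6% risk, the shortfall is worth 0.2 to 0.5 points. Counting or not counting heparin-phase events is worth about 0.9 points at an assumed 1% heparin-phase risk, and up to about 2.8 points at an extreme 3%. Each misassigned event is worth 1.4 points. These sizes rest on heparin starting at diagnosis and on event risks that the protocol does not give.

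A reader might set the lowest and highest rates side by side and infer that one cohort could yield anything from 5.5% to 8.7%. That is not supported: the low figure belongs to patients with 15 heparin days and the high one to patients with 5. For fixed patients the spread is 5.5% to 8.4% or 5.8% to 8.7%, and only at the 3% extreme. Sampling error remains the larger uncertainty. The change is still worth making because the ambiguity lies outside the confidence interval and costs little to remove.

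**What to change.** 1. In sections 5.1.1 and 6, set time zero for the primary endpoint at the first DOAC dose.
2. In section 5.1.1 and Appendix B, state that only new or expanding bleeding and new or recurrent VTE after that dose count. Report events between diagnosis and first dose separately.
3. In section 5.2, time the last outcome contact so that it reaches 6 months from the first dose. A telephone interview, which section 5.2 already allows, is enough.
4. Record the dates of first dose and consent. As sensitivity analyses only, show a delayed-entry Kaplan-Meier estimate (entry at the later of first dose and consent) or an analysis of patients enrolled during the initial hospitalization. Neither should be primary, since each gives up early person-time or patients in an already small cohort.

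**Cost.** The final contact falls 5 to 15 days later, or one extra call is needed per patient (at most 69 calls for 69 patients). The case report form needs at most one or two date fields. A patient who has started the DOAC and enrolled by June 2027 still reaches 6 months from first dose by December 2027, so the timetable in section 5.3 holds. The change affects measurement and analysis only, not treatment.

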## 1. INTRODUCTION AND RATIONALE

CVT accounts for only 0.5-1% of all diagnosed and treated stroke cases worldwide. Previous studies have demonstrated that patients with CVT typically exhibit distinct clinical characteristics compared to those with other types of stroke. Notably, disproportionately affects younger individuals, with the majority of cases occurring in patients under 50 years of age and approximately two-thirds involving women. Clinically, CVT often presents with symptoms associated with elevated intracranial pressure or focal brain parenchymal lesions, which may or may not be associated with mass effect.

Current international guidelines uniformly recommend initiating treatment with low-molecular-weight heparin (LMWH) or unfractionated heparin during the acute phase. Once the clinical status and imaging findings have stabilized, oral anticoagulation is advised for a duration of 3-12 months, depending on the patient's individual risk profile.

In recent years, increasing attention has been directed toward the safety and efficacy of DOACs in the management of CVT. The first randomized controlled trial (RCT) evaluating DOAC use in CVT was the RESPECT-CVT trial, published in 2019, which assessed dabigatran. This was followed by CHOICE-CVT, was conducted in China. Both studies compared dabigatran with vitamin K antagonists (VKAs) and found no significant differences in safety and efficacy between the two groups. In 2023, the SECRET trial - an RCT comparing rivaroxaban with VKA - reported comparable outcomes. However, due to the rarity of CVT, all of these RCTs were limited by relatively small sample sizes, underscoring the inherent difficulty of conducting large-scale RCTs for rare conditions.

To complement these findings, large multicenter observational studies have been undertaken. Notably, the ACTION-CVT and DOAC-CVT studies have provided real-world evidence supporting the use of DOACs, demonstrating comparable safety and effectiveness to VKAs. DOACs also offer several practical advantages, including fixed dosing, fewer drug-food interactions, and no requirement for routine INR monitoring. Nevertheless, even these observational studies have not enrolled patient numbers in the thousands, thereby limiting the statistical power for robust subgroup analyses.

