### **5.3. Sample size**

Due to the rarity of the disease and the single-center design of the Treatment Outcomes of DOACs in CVT study, a minimum of 69 patients are expected to be enrolled over a 2-year period starting in June 2025. Patient recruitment is anticipated to be completed by June 2027, with final 6-month follow-up assessments expected to conclude by December 2027.

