## **6. STATISTICAL ANALYSES**

All statistical analyses will be conducted using R software (version 4.4.1). Statistical significance will be set at a two-sided p-value < 0.05.

Descriptive statistics will be used to summarize baseline characteristics. Continuous variables will be reported as means  $\pm$  standard deviations (SD) or medians with interquartile ranges (IQR), depending on distribution. Categorical variables will be expressed as counts and percentages.

The primary endpoint: a composite of major bleeding (per ISTH criteria) or symptomatic recurrent venous thromboembolism (VTE), including cerebral venous thrombosis, deep vein thrombosis, pulmonary embolism, or splanchnic vein thrombosis—will be analyzed as a time-to-event outcome. Kaplan–Meier survival curves will be constructed, and group comparisons will be performed using the log-rank test. Cumulative event rates at 6 months will be reported with 95% confidence intervals.

For secondary endpoints, the following analyses will be conducted:

- Functional outcome (mRS 0-1 vs 2-6 at 3 and 6 months) will be analyzed using logistic regression to identify predictors of favorable recovery.

- Venous recanalization status at 6 months will be described as complete, partial, or absent, based on follow-up imaging, and summarized as proportions.
- Rates of major bleeding, any bleeding, symptomatic recurrent VTE, and arterial thrombotic events will be summarized descriptively and reported with 95% confidence intervals.
- Health-related quality of life (EQ-5D-5L), chronic post-CVT headache (HIT-6), at 3 and 6 months will be compared using paired t-tests or Wilcoxon signed-rank tests, as appropriate.
- Changes in D-dimer levels from baseline to follow-up will be analyzed using paired tests and visualized longitudinally.

Missing data will be handled using complete case analysis. If the missing rate exceeds 10% for any variable, sensitivity analyses will be performed.

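### The chronic headache definition sets frequency and duration but not new onset or worsening, so headache that was already chronic before the CVT would count as chronic post-CVT headache

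*Protocol*

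**What the plan says.** The only definition is in Protocol section 5.2, among the data collected at the 3- and 6-month follow-up: "Presence of chronic headache, defined as a headache occurring on" at least 15 days per month and "persisting for more than 3 months following the acute CVT event". The protocol adds that this is consistent with ICHD-3. Headache-related disability (HIT-6) is listed in the same place.

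Section 5.1.2 lists the endpoint at 6 months (± 1 month) as "Frequency of chronic headache following CVT". Section 6 uses the label post-CVT and plans only a comparison between the two follow-up times: "chronic post-CVT headache (HIT-6), at 3 and 6 months will be compared".

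For baseline, section 5.2 asks for clinical and radiological data, "including patient demographics, risk factors, imaging findings, anticoagulant treatment details, and in-hospital events during the acute phase of CVT". Headache history and a pre-CVT HIT-6 score are not named. Section 4.3 has no exclusion for prior chronic headache; its last criterion is "Patients already receiving anticoagulation therapy for another underlying condition at the time of CVT diagnosis".

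**The concern.** The time element in the definition says how long the headache must last after the CVT. It does not say when the headache began. Someone who had headache on 15 or more days per month for years before the CVT, and still has it at 6 months, meets every stated condition although the CVT changed nothing.

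Readers are likely to take a frequency labelled post-CVT headache as a sequela of the disease. This is a single cohort with no headache control group, so the natural reference is the patient's own earlier status, and the protocol does not name it. Section 6 does plan a baseline comparison for D-dimer, but none for headache. Section 1 describes CVT patients as mostly under 50, with "approximately two-thirds involving women". That makes some background headache plausible, but it is not evidence of how much, and the point does not depend on it.

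**Working it through.** **Text check.** There are four places where prior headache could be separated out.

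| Place in the Protocol | What it fixes | Separates prior headache? |
|---|---|---|
| 5.2, definition | at least 15 days per month, for more than 3 months after the CVT | No |
| 5.2, baseline data | an open list that does not name headache | Not as listed |
| 4.3, exclusions | no criterion on headache | No |
| 6, analysis | HIT-6 at 3 months against 6 months | No pre-CVT reference |

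**Illustration of size.** The protocol states no figure for this endpoint, so there is none to reproduce. The only documented input is N = 69 (section 5.3: "a minimum of 69 patients are expected to be enrolled over a 2-year period"). Two inputs are assumed and varied:
- p_pre: proportion with chronic headache before the CVT that persists to 6 months.
- p_new: rate of new chronic headache among the others.

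Formulas:
- Expected pre-existing cases counted = 69 × p_pre
- Chance of at least one = 1 − (1 − p_pre)^69
- Reported frequency = p_pre + (1 − p_pre) × p_new
- Excess relative to p_new = reported frequency / p_new − 1

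| p_pre | Expected cases of 69 | Chance of at least one | Reported frequency if p_new = 10% |
|---|---|---|---|
| 1% | 0.7 | 50% | 10.9% |
| 2% | 1.4 | 75% | 11.8% |
| 5% | 3.5 | 97% | 14.5% |
| 10% | 6.9 | >99% | 19.0% |

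The relative excess depends strongly on p_new:
- p_new = 10%: 0.02 + 0.98 × 0.10 = 11.8% and 0.05 + 0.95 × 0.10 = 14.5%, which is 18% to 45% above 10%.
- p_new = 25%: 0.02 + 0.98 × 0.25 = 26.5% and 0.05 + 0.95 × 0.25 = 28.75% (28.8%), which is 6% to 15% above 25%.

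The formulas assume that all 69 patients are assessed and that every prior case stays at 15 or more days per month. If some prior cases improve, the excess is smaller. If some worsen after the CVT, counting those is defensible, and the excess is again smaller.

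**The case against.** Five arguments can be made against the point.

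1. *The baseline list is open and the case report form is not shown.* This stands. A reader might infer that prior status is not recorded and that the count can never be corrected. The documents support only that it is not listed. Patients are also contacted at 3 and 6 months, so they could be asked then. But even if the history is recorded, the definition does not use it.

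2. *The ICHD-3 reference may bring in a condition of attribution or of new onset.* What ICHD-3 requires cannot be checked from the protocol, so it would be too strong to say that no such condition is intended. The protocol itself spells out only frequency and duration. If more is meant, it needs writing down, or assessors may classify the same patient differently.

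3. *After, following and post are words of time, and the frequency of any chronic headache after CVT is a legitimate measure of burden.* This stands in part. The protocol makes no explicit causal claim, and the figure is too high only if the target is new or worsened headache. The protocol does not say which target it means, while its label invites the second reading. Keeping the overall frequency and adding a split serves both.

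4. *The shift lies within sampling error.* At an assumed 10% new-onset rate the shift is 1.8 to 4.5 percentage points, while the 95% Wilson interval for 7 of 69 is about 5.0% to 19.5%. That is correct and limits the practical weight. However, wrongly counted prior cases move the estimate in one direction only, and a larger sample would not remove that.

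5. *This detail belongs in a statistical analysis plan.* The definition is already fixed in the protocol, and an analysis plan cannot supply a history that was not collected.

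**Conclusion.** The point holds on the text. As written, unchanged pre-existing chronic headache is counted in the frequency of chronic post-CVT headache, and no listed baseline item allows it to be separated.

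The size is unknown, because the protocol gives neither a prior prevalence nor an expected frequency. The range of 0.7 to 6.9 patients of 69 rests on an assumed 1-10% prior prevalence. The relative excess, at an assumed 2-5%, runs from 6% to 45% depending on the new-onset rate, so no single percentage should be quoted as the bias.

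The consequence is limited to the interpretation of one descriptive secondary endpoint. The primary composite and the sample size are untouched. The change is worth making because it is cheap and recall of the pre-CVT period weakens with time.

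**What to change.** Add one baseline item to the case report form: headache days per month in the 3 months before onset of the CVT symptoms. Anchor it to symptom onset, not diagnosis. Section 1 notes that CVT often presents with symptoms of raised intracranial pressure, so headache shortly before diagnosis may already be due to the CVT.

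In section 5.2, keep the overall frequency of chronic headache at 6 months and report it in three rows:
- (a) new chronic headache: fewer than 15 days per month before the CVT;
- (b) pre-existing chronic headache that worsened;
- (c) pre-existing chronic headache, unchanged.

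Label only (a) and (b) as post-CVT headache, and state in advance how worsening is judged. A simple rule that counts only patients who cross from below 15 to 15 or more days would lose group (b). If the ICHD-3 reference is meant to add a condition beyond frequency and duration, write that condition out.

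The cost is one history question and a few lines in section 5.2, with no added procedure. The downside is recall error in the pre-CVT count. Patients already enrolled can be asked at their 3- or 6-month contact, with somewhat more recall error.
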